### **Introduction**

Up to 72% of adolescents with ADHD experience sleep problems.[1] A systematic review by Lunsford-Avery and colleagues (2016) and a meta-analysis done by our research group show that adolescents with ADHD have a more disrupted sleep and experience more sleep problems compared to their typically developing peers.[2,3] This is particularly concerning, because disrupted sleep is related to worsened clinical, neurocognitive, and functional outcomes in adolescents with ADHD and leads to increased ADHD symptom impairment.[4] Therefore, more information on the effectiveness of sleep interventions specifically for adolescents with ADHD would be beneficial and may inform treatment guidelines for ADHD, as these often note problems in sleep in ADHD but lack evidence supporting specific intervention guidelines for ADHD.[5,6] Although it is still unclear which factors underly worsened sleep and sleep problems in adolescents with ADHD, inadequate sleep hygiene practices are likely to be an important factor.[7] Sleep hygiene entails various modifiable factors and behaviors that influence sleep (i.e. sleep practices, physiological factors like caffeine and alcohol use, sleep environment) and thus is an important intervention target to improve disrupted sleep.

Up to now, there is no evidence-based cognitive behavioral treatment (CBT) aimed at improving sleep specifically for adolescents with ADHD. A proof of principle is available in children with ADHD,[8-12] in typically developing adolescents,[13,14] and in adults with ADHD and sleep problems.[15] However, treatments for adolescents with ADHD have received little attention so far. This might be due to the difficulty of providing treatment for adolescents in general and adolescents with ADHD in particular. For children with ADHD parent-mediated interventions have been proven to be effective. However, they generally do not work for adolescents due to a growing need for autonomy.[16] Furthermore, adolescents with ADHD are known to have motivational difficulties, which are seen by enhanced treatment drop-out and non-compliance to treatment.[17] Moreover, they have severe problems with planning and organization in daily life,[18] and resisting immediate temptations.[19] These difficulties are likely to affect their sleep; due to organizational difficulties they do not manage to get enough sleep, or may not be able to resist immediate temptations such as mobile phones or social media. Given the specificity of this developmental phase in ADHD, interventions may need to be adapted both towards the developmental phase and the disorder. Therefore, experts in the field of sleep, psychopathology and functional disabilities recommend that sleep disorders should be treated together with functional disabilities such as ADHD symptoms, as they are interactively and bidirectionally related to each other.[20,21]

Recently, one small scale pilot study has been published that shows that the existing CBT based Transdiagnostic Sleep and Circadian Intervention for Youth [TranS-C][22] resulted in improvements in sleep, mental health symptoms, and daily life executive functioning in 14 adolescents with ADHD.[23] However, the parents of the participants were all highly educated and participants themselves were very motivated, which is likely not to be a representation of all adolescents with ADHD.[23] Thus, there still is a clear need for a sleep treatment specifically developed for adolescents with ADHD, tailored to their specific difficulties with motivation and

planning and organization. Therefore, our lab developed a CBT intervention that integrates sleep training with motivational interviewing, and planning/organizational skills with the aim of improving sleep problems in adolescents with ADHD.[24,25] The acronym is SIESTA [Sleep IntervEntion as Sympom Treatment for ADHD]. To tailor the intervention optimally towards the needs of adolescents with ADHD and enhance feasibility of the assessment and study protocol of our RCT, we piloted our SIESTA intervention and the study protocol in eight adolescents with ADHD and sleep problems.[26] Fine-tuning of the intervention and study protocol was based on the outcomes of the pilot study and feedback from adolescents with ADHD and parents from focus groups.

[figure not shown]
The objective of this study is to test the effectiveness of SIESTA in combination with treatment as usual (TAU) for ADHD symptomatology compared to TAU only in a randomized controlled trial. SIESTA is expected to improve sleep architecture measured both objectively and subjectively; specified as total sleep time (TST), sleep onset latency (SOL), sleep efficiency (SE), and number of awakenings (NoA), sleep problems and sleep hygiene practices (primary outcomes). Regarding secondary outcomes SIESTA is expected to improve ADHD symptoms, comorbid symptoms and functional outcomes. Both primary and secondary outcomes are expected to show greater improvement in the SIESTA group, both on the short (post-test) and middle long term (approximately three months follow-up), than in the TAU only group.

## **Methods and analysis**

### **Study design**

A randomized, controlled, investigator blinded monocenter trial is used to test whether SIESTA in combination with TAU results in greater improvement in sleep than TAU only in adolescents with ADHD. This trial was pre-registered at ClinicalTrials.gov (Identifier: NCT04723719; all items from the World Health Organization Trial Registration Data Set are further elaborated on in this registration) and we adhered to the SPIRIT recommendations when drafting this protocol (see Supplement 1).[27] This study consists of five waves of recruitment, always following the same procedure (see Figure 1); January-March 2021, September-October 2021, January-March 2022, September-October 2022, and January-March 2023. We aimed to be outreaching and provide treatments close to where the adolescents live, therefore our therapists travel to different locations in Flanders (Leuven, Antwerp, Hasselt, Brussels, Gent, and Roeselare). These different locations in rural and urban areas are chosen to remove barriers for accessibility and to be able to include a diverse sample.

**Figure 1**  
Study procedure

*Note.* K-SADS = Kiddie Schedule for Affective Disorders and Schizophrenia for school aged children (6-18 years) Present and Lifetime version based on the DSM-5;[28] WISC = Wechsler Intelligence Scale for Children, fifth edition;[29] WAIS = Wechsler Adult Intelligence Scale, fourth edition;[30] SIESTA = Sleep IntervEntion as Symptom Treatment for ADHD; TAU = treatment as usual.

a Those randomized to TAU can voluntary choose to receive SIESTA after the last follow-up. These treatments after the last follow-up are not part of the study protocol anymore.

### Participants

Inclusion and exclusion criteria can be found in Table 1.

**Table 1***Inclusion and exclusion criteria*

Inclusion	Exclusion

 
• 13 - 17 years old
 
• Attending secondary education
 
• ADHD diagnosisa
 
• Sleep problemsb: (<math>\geq 3</math> days/week and lasting <math>\geq 3</math> months) 
 
○ Sleep onset > 20 min
 
○ and/or wake up time after sleep onset > 30 min
 
○ and/or < 7h sleep
 
○ and at least one inadequate sleep hygiene practice
 
○ and distress reported by adolescent and/or parent
 
 
 
• IQ <math>\geq 80^c</math>
 
• Stable use of ADHD medication (4 weeks before screening)
 
	
 
• Comorbid disorders: 
 
○ Conduct disordera
 
○ ASDd
 
○ Depressive disorder with suicide risk or active suicidalitya
 
 
 
• Sleep disordersb: 
 
○ Narcolepsy
 
○ Sleep breathing disorder
 
○ Restless leg syndrome
 
 
 
• Substance abusee (except nicotine), however substance use is not an exclusion criterion
 
• Physical or medical problems (and medication) causing sleep problems
 
• Medication for sleep, anxiety or depression
 
• Melatonin use (2 week washout of melatonin before participation)
 
• Acute crisis situation at home
 
• CBT sleep intervention participation (< 6 months ago)
 

*Note.* a Verified by the semi structured interview K-SADS-PL DSM-5 with the parents;[28]

b Determined in an extensive sleep interview based on the DSM-5 and ICSD-3 criteria with parents and adolescents;[20,31]

c Verified by the subtests Vocabulary and Matrix reasoning from the Wechsler Intelligence Scale for Children for adolescents aged 13 to 16 years old or the Wechsler Adult Intelligent Scale for adolescents aged 17 years old;[29,30]

d As indicated by the parents;

e Verified by the subscale 'Disorders in the use of substances and behavioral addictions' of the Measurements in the Addictions for Triage and Evaluations - youth (MATE-Y).[32]

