### **Secondary outcomes**

**ADHD symptoms.** Inattention and hyperactivity-impulsivity subscales of the Disruptive Behavior Disorder Rating Scale (DBDRS) are used to measure ADHD symptoms.[48] This parent-reported questionnaire is validated, and the internal consistency of the scales in a Flemish sample is good for inattention and hyperactivity-impulsivity.[48]

**Comorbidities.** Symptoms of multiple comorbidities are measured using self-, parent- and teacher-report questionnaires. The ODD subscale of the parent-reported DBDRS is used.[48] To evaluate symptoms of anxiety, the SCARED-R is administered.[49] The SCARED-R is a validated, self-report questionnaire with good psychometric properties.[50] The self-reported Child Depression Inventory 2 (CDI-2) is administered to assess depressive symptoms.[51] Again, this is a validated questionnaire with good internal consistency ( $\alpha = .88$ ).[51]

**Functional outcomes.** Parent-adolescent conflict is measured using the Conflict Behavior Questionnaire (CBQ).[52] This is a validated, parent-report questionnaire with acceptable to good internal consistency (appraisal of parent;  $\alpha = .73$ ; appraisal of dyad;  $\alpha = .89$ ).[53] To evaluate adolescents' educational achievement, parents complete the Homework Problems Checklist (HPC)[54] and teachers the Classroom Performance Scale (CPS).[55] Both questionnaires are validated and have an excellent internal consistency (HPC:  $\alpha$  ranging from .90 to .92; CPS: academic competence;  $\alpha = .98$ ; interpersonal competence;  $\alpha = .91$ ).

Additionally, exploratory at baseline two questionnaires are assessed as potential moderators; the self-rated Quick Delay Questionnaire (QDQ [58]) and the parent/guardian views on neuropsychological (dys)functioning of their adolescents (the Cognition And Motivation in Everyday Life; CAMEL [59]).

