The informed consent (parent(s)/guardian(s)/guardians) /assent (adolescent) will be send to the participants before the first meeting and they are required to sign it and send it back via email. In case of questions, the researchers are available via the phone and any uncertainties can be discussed during the first meeting. During the first meeting it is assessed whether the adolescent meets inclusion criteria for the study. In this session the K-SADS (parent(s)/guardian(s)) and the sleep interview (adolescent and parent separately) are conducted, either face-to-face or via Mynexuzhealth (or via the platform of PraxisP, backup Skype for Business). Then, the HSDQ and the subscale "Disorders in the use of substances and behavior addictions" of the MATE-Y and the SCARED are administered via Qualtrics. Next 2 subtests of the WISC/WAIS (vocabulary and matrix reasoning) are administered. Further, the adolescent is explained about the wrist actigraphy and sleep logs that need to be recorded in the next week. To remind them to fill out the sleep diary from the previous night, messages will be send when they arrive from school or other activities. Phone numbers of the participants will be stored in a separate password protected excel document on our secure network drive with only the participant number as reference. Using phone numbers exclusively requested for this study, reminders to fill out the sleep diary will be sent. In the phones, which are password protected, no names will be stored, only the participant numbers. When there is a COVID-19 outbreak, an appointment is made so that a courier service can bring the actigraphs to the adolescents. Before and after use, they will be disinfected. Another appointment will be made for one week later when either the researchers or the courier service will collect the actigraph at the home of the adolescent. The reason for not letting the adolescents send back the actigraph is that they are a very specific population. They have great problems with planning and organization. Thus, to prevent that the actigraphs are not send back or get lost, they will be picked up. Within one week after collection of the actigraph the psychologist of the study informs the adolescents and his/her parent(s)/guardian(s) whether he/she meets inclusion criteria for the study. After the screening, feedback in the form of a summary of the obtained data will be given to involved clinicians. This data will concern relevant information for the clinician giving the treatment, namely a summary of the sleep- and K-SADS interview and the results of the questionnaires (HSDQ, and MATE-Y).

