
When the adolescent meets inclusion criteria, the adolescent has to fill out the pretest questionnaires in Qualtrics. Parent(s)/guardian(s) of the adolescent are also asked to answer questionnaires in Qualtrics; also, they are asked to mail the link of the questionnaire (CPS) in Qualtrics to the teachers of the adolescent for their evaluation of the adolescent. Moreover the teacher will be asked how many lesson times per week he/she has contact with the participant. The names of the teachers will not be known by the researchers.

After the pretest is conducted, appointments for the treatment are made. However, participants are informed that those appointments can either happen as planned or that the treatment will take place 6 months later, due to the condition their child was assigned to. To avoid the possibility of a systematic bias in the assignment of participants to both groups (SIESTA treatment and treatment as usual (TAU) versus TAU only), randomization happens. We will use a stratified permuted block randomization based on medication use (yes/no) in blocks of 2 participants whereby an independent researcher performs the randomization. After the last treatment session, both the adolescent who followed the treatment and the paired adolescent from the TAU-group, are contacted by the researchers and provided with the actigraphs. The daily sleep logs are again filled out in Qualtrics. Within one week after the last treatment session a posttest session is planned in which the adolescent and parent(s)/guardian(s) are asked to fill out the questionnaires in Qualtrics. Filling out the questionnaires should not take longer than 1 hour for any informant. The actigraphs will again be picked up by a researcher or the courier service. The same procedure is applied during the follow-up measure after 3 months, including the actigraph/daily logs and the questionnaires. After follow-up, the treatment is provided to the adolescent in the TAU-group from that block.

In case of serious adverse events or a crisis situation, e.g. suicidality, during any phase of the study, (previously involved) clinicians will be contacted by the researchers. Also, if necessary at any time of the study, additional psychological aid can be given.

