### **Safety**

Recording of adverse events: The participant will be asked to report any adverse event related to the study-specific intervention to the study team. These reported events will be documented by the Investigator in the source documents.

The following minimum information should be recorded for each AR:

- AE description
- start and stop date of the AR
- severity
- seriousness
- causality assessment to the study interventions
- outcome

Reporting to the Ethics Committee

The sponsor will assess whether any relevant safety information that becomes available during the study should be reported ad hoc to the EC.

The sponsor has the obligation to, once a year throughout the clinical trial (or on request), submit a progress report to the EC containing an overview of all SARs occurred during the reporting period and taking into account all new available safety information received during the reporting period.

During the first two sessions of the intervention, participants can freely report any adverse event related to the study-specific intervention to their therapist. From the third session on the following question will be posed: "Has anything happened last week that was a danger to you? Like suicidal thoughts, risk-seeking for example bingedrinking, or anything like that.". We argue that posing this question best starts during the third session as during the first two sessions the main focus is on forming a relationship and building trust. However, asking this type of question is not a risk factor to elicit suicidal thoughts or behavior even in at-risk adolescents. Research shows that talking about suicide and idealization, reduces suicide and improves mental health (e.g. Dazzi et al., 2014).

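### The suicidality exclusion is verified with the parents only, with no written step for asking the adolescent before inclusion or for reviewing the CDI-2 before randomisation

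*Combined protocol and SAP*

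**What the plan says.** Table 1 (Participants) lists "Depressive disorder with suicide risk or active suicidality" among the excluded comorbid disorders and marks it with note a, which reads "Verified by the semi structured interview K-SADS-PL DSM-5 with the parents". The sleep criteria carry a different note, under which both parents and adolescents are interviewed.

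Ethics & procedure describes the same arrangement. Eligibility is tied to the first contact: "During the first meeting it is assessed whether the adolescent meets inclusion criteria for the study". On informants it says "In this session the K-SADS (parent(s)/guardian(s)) and the sleep interview (adolescent and parent separately) are conducted". The screening questionnaires are the HSDQ, a MATE-Y subscale on substance use and addictive behaviour, and the SCARED; the sentence ends "of the MATE-Y and the SCARED are administered via Qualtrics". The same section then says "When the adolescent meets inclusion criteria, the adolescent has to fill out the pretest questionnaires in Qualtrics".

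Secondary outcomes introduces the adolescent's own depression measure: "The self-reported Child Depression Inventory 2 (CDI-2) is administered to assess depressive symptoms". It appears there as an outcome and is not linked to eligibility.

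The Safety section schedules a direct question to the participant about danger, including suicidal thoughts, from the third treatment session. It defends the question on the ground that "asking this type of question is not a risk factor to elicit suicidal thoughts or behavior even in at-risk adolescents".

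**The concern.** Suicidality is largely an internal state, and the participants are 13 to 17 years old. A criterion checked only with parents can act only on what parents know. Elsewhere the plan takes internal states from the adolescent: anxiety and depressive symptoms are self-reported outcomes, while ADHD and oppositional symptoms are parent-reported. It also uses both informants for the sleep criteria. The one exclusion that concerns suicide risk does not follow that pattern.

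What is at stake is participant safety. An adolescent whose parents are unaware could be randomised to TAU, where SIESTA is offered about 6 months later, or could start SIESTA without the study team knowing. The point does not bear on power, the effect estimate or the mixed model.

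**Working it through.** No figure in the plan bears on this, so there is nothing to recompute. The check is to follow an adolescent through the written sequence and ask, at each stage, who is the informant and whether suicidality is provided for.

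| Stage (section) | Informant and content | Adolescent asked about suicidality? |
|---|---|---|
| First meeting, K-SADS (Participants, note a; Ethics & procedure) | Parents or guardians | No; the adolescent is not the informant |
| First meeting, sleep interview (same sections) | Adolescent and parent separately; described as covering sleep criteria | Not described; items are not reproduced |
| Screening questionnaires (Ethics & procedure) | HSDQ, MATE-Y subscale, SCARED | None is described as measuring depression or suicidality; the HSDQ is not explained |
| Inclusion result, within a week of collecting the actigraph (Ethics & procedure) | Study psychologist informs the family | No further check described |
| Pretest questionnaires (Ethics & procedure) | Adolescent and parents, once criteria are met | CDI-2 presumably here; no review step written |
| Appointments and randomisation (Ethics & procedure) | Independent researcher randomises | No |
| SIESTA sessions 1 and 2 (Safety) | Participant may volunteer intervention-related events | Not asked |
| SIESTA session 3 onward (Safety) | Scheduled question to the participant | Yes |
| TAU during the trial | No treatment sessions | No scheduled equivalent |

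Three observations follow.

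1. The parent-only K-SADS needs no inference. Note a and Ethics & procedure state it separately and agree.
2. The timing of the CDI-2 is inferred. It is missing from the screening list, it is an outcome measure, and pretest questionnaires follow the inclusion decision. No text names it in a particular battery, and Figure 1 is not shown. The inference is not essential. Because the pretest precedes the treatment appointments and randomisation is described after it, CDI-2 answers could exist before allocation. What is missing is any statement that someone reads them by then. The screening feedback to clinicians is limited to the sleep and K-SADS interviews, the HSDQ and the MATE-Y (Ethics & procedure; Confidentiality).
3. Safety considerations places the systematic assessment of adverse events within the treatment sessions, which is why TAU has no counterpart.

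On size: the expected number missed would be the number screened, times the share who meet the criterion, times the share of those whose parents are unaware. The documents give a planned enrolment of 92 to 100 (Participant recruitment) and none of these three factors, so no estimate is offered.

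**The case against.** The strongest reply is that silence is not absence. The adolescent has a separate and extensive interview based on DSM-5 and ICSD-3, and its items are not shown, so an interviewer may well ask about mood or risk. Clinic files are consulted for some participants (Where is the treatment provided?). Clinicians are contacted if suicidality arises in any phase of the study, and extra psychological help can be given at any time; this covers TAU, where usual care continues. The two descriptions of the K-SADS agree, so there is no contradiction to reconcile.

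Much of this stands, and it rules out several stronger readings that a reader might infer:

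- That no adolescent is asked about suicidality before inclusion. The documents show only that no section provides for it.
- That suicidality would be recognised only at session 3. Volunteered reports in the first two sessions and the crisis provision are earlier routes, although the former is limited to intervention-related events.
- That the trial knowingly enrols ineligible participants. Someone negative on the parent K-SADS has passed the check as written. The criterion can also be read as requiring a depressive disorder, in which case suicidal thoughts alone would not meet it.
- That the CDI-2 would settle the matter. The documents say only that it measures depressive symptoms, not that it has a suicidality item.

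The gap remains. The crisis provision acts once suicidality is known and does not screen. Files exist for only some participants, with content and informant unspecified. The Safety section's wish to build trust first explains when the question comes within therapy, not why eligibility relies on one informant.

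Timing also limits what a change can achieve. Some references were accessed in December 2022 and the last recruitment wave is January to March 2023, so an amendment to this version could reach at most that wave.

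**Conclusion.** The point holds as a gap in a stated verification rule. The exclusion is checked through parents alone, no written step puts it to the adolescent before inclusion, and no written step has the CDI-2 reviewed before randomisation. It can therefore miss adolescents whose parents are unaware of their suicidality. The procedure as written applies to every participant, but the number affected cannot be derived from the documents.

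The conclusion about the K-SADS rests on explicit text. The conclusion about the CDI-2 rests on its absence from the screening list and on the lack of any review step; Figure 1 could change the timing but would not by itself supply a review. The plan's own position that asking does no harm removes the obvious reason for leaving the question until treatment. This is an inexpensive safety improvement that should be made, not a flaw that undermines the trial's analysis.

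**What to change.** Amend note a of Table 1 and the first-meeting paragraph of Ethics & procedure so that the adolescent is also an informant for this existing criterion, using the separate interview already held at that meeting. In the pretest paragraph of the same section, state when the CDI-2 is completed and that its answers are reviewed before randomisation.

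How differing parent and adolescent reports are resolved, and what action follows, is for the sponsor's clinicians to decide; no rule is proposed here. Adding an informant may change who is excluded, and the amendment should say so.

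The cost is a few minutes per participant, reading a questionnaire that is already collected, possibly a few more screen failures, and a short ethics amendment. If recruitment closes before the amendment takes effect, the trial report should state that this criterion was verified through parents.
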